administrations. This criterion is necessary to permit selection of the necessary treatment and generalization probe items as described below, and will minimize ceiling effects on the naming probes. Fourth, in order to avoid enrolling into the study participants who have profound naming impairments and are therefore unlikely to benefit from the study treatment (e.g., patients with global aphasia and/or verbal output limited to recurrent stereotypy), all participants must obtain a CAT Naming modality T-score greater than or equal to 40. Finally, we will exclude from participation potential participants with severe motor speech disorder (i.e., apraxia of speech and/or dysarthria). Motor speech diagnosis and severity judgments will be made by study investigators with experience in this area ([name], [name], [name]), based on the following samples of behavior: Connected speech samples (described below); three recorded attempts at laryngeal diadochokinesis at slow, medium, and fast rates; three trials of maximum sustained phonation; and recorded responses to the three subtests of the Apraxia Battery for Adults-2, including Speech Diadochokinesis, Repetition of Words of Increasing Length, and Word Repetition with Repeated Trials. Two judges will independently diagnose and rate the severity of motor speech disorder in each potential participant. A third judge will provide a diagnosis and rating to resolve any disagreements regarding presence or severity of motor-speech disorders. Chart review of PIRATE participants to date suggests that the above additional five criteria would have excluded approximately 20% of the unique veterans served by the program. Thus, out of 72 patients who will be seen in PIRATE over the four-year duration of the project, approximately 58 should be eligible for enrollment in the study. Of these 58 eligible veterans, it is reasonable to expect that at least 50 will enroll in the study and complete the treatment and all study visits (including follow-up visits). This sample size should be sufficient for detecting the relationships between treatment response, psycholinguistic profile, and cognitive performance relevant to Specific Aim 1, and to detect differences relevant to testing the dose-response hypotheses in Specific Aim 2.

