Some participants may also have co-occurring conditions which would prevent them from participation in the imaging arm of the study (claustrophobia; presence of metal in the body). These participants will be enrolled in the study but will not complete imaging procedures. A chart review of PIRATE participants to date indicates that approximately 20% of veterans enrolled in PIRATE may have such exclusionary criteria: roughly 17% report pacemaker or other implanted metal objects or devices incompatible with MR scanning. Thus, the participant sample used to address the neuroanatomical hypotheses proposed under Specific Aim 1 may be smaller than the sample contributing data the other proposed analyses. Under the worst case scenario of no overlap between these imaging-related exclusionary criteria and those described in the preceding paragraph, we expect to obtain a sample size of 40 participants (50 minus 20%) to conduct the proposed imaging-related analyses. As described in section C.3.1.3 below, this sample size should be sufficient to detect the relationships relevant to the neuroanatomical hypotheses.

C.2 Procedures

The schedule of procedures for participants enrolling in the study is summarized in the flowchart in Figure 4. Participants enrolling in the research study will receive a single pre-treatment structural MRI and a battery of cognitive assessments at program entry (see section C.2.3 below). They will also have their performance on standardized measures of naming and other language functions assessed repeatedly throughout the protocol (see section C.2.2 below), and they will receive an intensive dose of a treatment (SFA) designed to target lexical-semantic processes (see section C.2.1 below). Participants' performance on treated and untreated lexical items will be probed three times weekly, to assess acquisition and generalization and to decide when participants will move to a novel set of treatment exemplars.

Half the participants will be randomly assigned to a delayed-treatment condition. The purpose of this condition is to provide an additional measure of experimental control, to ensure that any observed improvements are not due simply to the social contact afforded by the residential component of the treatment program. Previous work [7] has found that simple exposure or engagement in the absence of specific therapy

[figure not shown]

Figure 4: Testing and treatment procedures for study participants

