All participants will also be administered a set of cognitive assessments immediately prior to program entry. These cognitive tasks will include measures of executive function abilities, visuospatial skills, recognition memory, and tasks of sustained and divided attention. The WCST and the picture and word versions of the Pyramids and Palm Trees Test (PPT) will be administered to assess executive function skills. The PPT was found to correlate with the cognitive factors identified in Lambon Ralph et al.'s study and performance has been shown to depend partially on reasoning and problem-solving abilities^[103]. Additionally, two of the studies found significant correlations between PPT performance and treatment response following naming therapy^[10].

^{66]}. The immediate and delayed recall of the Complex Rey Figure will be administered to evaluate visuospatial abilities and memory. This test has been found to be significantly correlated with naming treatment outcomes^[10]. Two of the short recognition subtests of the Camden Memory Test, the topographical and word subtests, will be administered to assess recognition memory^[66]. Additionally, study participants will be given the sustained and divided attention subtests of the TEA. As noted above, Lambon Ralph and colleagues^[10] found that the elevator counting with distraction subtest on the TEA was one of the significant cognitive factors that predicted naming treatment outcome. The TEA provides an aphasia-friendly, ecologically valid assessment of multiple forms of attention that has been standardized on a group of stroke patients^[104].

Finally, participants will receive structural magnetic resonance imaging scans immediately prior to program entry. Not all participants will be eligible to take part in imaging procedures (due to presence of exclusionary conditions such as claustrophobia or metal in the body). As noted above, current estimates are that approximately 20% of PIRATE participants to date have such exclusionary conditions.

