To determine whether the proposed sample size will be sufficient to detect the lesion-behavioral correlations described above, a power analysis was carried out on the correlational data from Parkinson and colleagues^[21]. The correlation coefficients reported by Parkinson range from 0.65 to 0.85. Power analysis indicates that a sample size of 40 will provide power >0.99 for detecting effects of this magnitude and power of 0.80 for detecting correlations with r values of 0.38 or greater. Given the likely greater variability among the patients who participate in PIRATE, both in terms of their demographic characteristics and their language impairment profiles, we anticipate that any correlations between neuroanatomical markers and language performance and recovery may be somewhat weaker than those observed in the Parkinson and colleagues study^[21], which had a much more uniform sample. However, the projected sample size of 40 should be sufficient to detect weaker correlations than those observed by Parkinson and colleagues^[21].

If no significant correlations are found between the above ROIs and change scores for the outcome measures, we will perform additional VLSM analyses to examine the relationship between lesion site and extent and treatment response in subgroups of study participants. Since participants in this study will likely be more heterogeneous than those in previous studies, the data from the current study may be noisier due to greater inter-subject variability. To explore the effects of this variability on neural correlates of treatment response, participants will be divided by aphasia severity, their CAT T-scores, since different aphasia severities may be associated with different responses to treatment^[1]. Additional analyses may explore the lesion-treatment relationships found in different subgroups of veterans.

C.3.2 Dose-response analyses

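### The imaging sample of 40 is labelled a no-overlap worst case, but it is the independence case; with no overlap the plan's rates give about 37 to 38 (wrong as written, minor)

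*Combined protocol and SAP*

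**What the plan says.** Section C.1 (Study participants) reaches the imaging sample in three steps.

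- **Study eligibility.** A chart review suggests that the five additional study criteria "would have excluded approximately 20% of the unique veterans served by the program". Hence "out of 72 patients who will be seen in PIRATE over the four-year duration of the project, approximately 58 should be eligible", and of these "it is reasonable to expect that at least 50 will enroll in the study and complete the treatment and all study visits".
- **Imaging eligibility.** A chart review indicates that "approximately 20% of veterans enrolled in PIRATE may have such exclusionary criteria". Section C.2.3 repeats the rate on the same base: "approximately 20% of PIRATE participants to date have such exclusionary conditions".
- **Combination.** "Under the worst case scenario of no overlap between these imaging-related exclusionary criteria and those described in the preceding paragraph", the plan says, "we expect to obtain a sample size of 40 participants (50 minus 20%) to conduct the proposed imaging-related analyses".

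Section C.3.1.3 (VLSM) uses that number. At n = 40 it states power above 0.99 for correlations of 0.65 to 0.85 and power of 0.80 for correlations of 0.38 or greater. It concludes that "the projected sample size of 40 should be sufficient to detect weaker correlations than those observed" in the cited lesion study.

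**The concern.** The assumption named in C.1 and the arithmetic beside it do not match. If nobody is caught by both sets of exclusions, the study criteria remove none of the veterans who cannot be scanned. All of them remain in a pool that has shrunk by a fifth, so their share of that pool must exceed 20%. Taking 20% off the 50 carries a programme-wide rate unchanged into the eligible group, which is correct only if the two exclusions are independent.

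At stake is how the 40 is read. Calling it a worst case presents it as a lower limit, and it is the only sample size behind the power statement for the neuroanatomical hypotheses. The statement of 0.80 power at r = 0.38 is quoted at exactly that n, so it has no slack. C.3.1.3 itself expects correlations somewhat weaker than those in the cited study.

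**Working it through.** **Inputs**

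- Veterans seen in PIRATE: 72 (C.1).
- Excluded by the study criteria: about 20% of PIRATE veterans (C.1), so 72 x 0.80 = 57.6 eligible, printed as 58.
- Enrolled and completing: at least 50 (C.1).
- Unable to be scanned: about 20% of PIRATE veterans (C.1, repeated in C.2.3), so 72 x 0.20 = 14.4.
- Power statement: n = 40, with 0.80 power at r = 0.38 (C.3.1.3).

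**The plan's figure**

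50 x (1 - 0.20) = 40.0. The printed arithmetic reproduces.

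**What overlap that figure implies**

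Let f be the share of unscannable veterans who also fail the study criteria. Among eligible veterans the unscannable share is 0.20(1 - f)/0.80, so

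N = 50 x [1 - 0.20(1 - f)/0.80].

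| Overlap | f | Unscannable share of eligible | N |
|---|---|---|---|
| None | 0 | 25% | 37.5 |
| Independence | 0.20 | 20% | 40.0 |
| Half | 0.50 | 12.5% | 43.75 |
| Full | 1 | 0% | 50 |

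The value 40 belongs to f = 0.20. For the stated scenario, f = 0: 14.4/57.6 = 25% and N = 37.5. With the rounded 58 eligible, 14.4/58 = 24.8% and N = 37.6.

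**Dependence on who completes**

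The 37.5 assumes that the 57.6 - 50 = 7.6 eligible veterans who do not complete have the same imaging-exclusion rate as those who do. The no-overlap extremes are:

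- no non-completer is unscannable: 50 - 14.4 = 35.6;
- every non-completer is unscannable: 50 - (14.4 - 7.6) = 43.2.

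**Effect on C.3.1.3**

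The plan states neither alpha nor sidedness, so alpha = 0.05 is assumed. Fisher z power is Φ(atanh(r) x √(n - 3) - z for alpha); a noncentral-t calculation is given beside it.

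| n | r = 0.38, one-sided Fisher z | r = 0.38, one-sided noncentral t | r = 0.38, two-sided Fisher z | r = 0.65, one-sided / two-sided Fisher z |
|---|---|---|---|---|
| 40 | 0.785 | 0.818 | 0.682 | 0.999 / 0.997 |
| 38 | 0.765 | 0.799 | 0.658 | 0.998 / 0.996 |
| 37 | 0.754 | 0.790 | 0.645 | 0.998 / 0.995 |

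The one-sided columns bracket the plan's 0.80 at n = 40. In them, power at r = 0.38 falls by about 2 points at n = 38 and about 3 points at n = 37.

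Holding alpha and power fixed and scaling the plan's own threshold: atanh(0.38) = 0.400; 0.400 x √(37/34.5) = 0.400 x 1.036 = 0.414; tanh(0.414) = 0.39.

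**The case against.** The strongest reply is that the inputs do not support this precision. The rates are described as approximate, and 50 is itself a lower expectation. C.1 itemises only a 17% component for implanted metal. Used alone with no overlap, that gives 50 x (1 - 0.17/0.80) = 39.4, close to 40. If the chart review covered the 53 veterans that B.1.1 reports as served (an assumption), one veteran more or fewer moves the no-overlap N by 50 x (1/53)/0.80, about 1.2. The shift of 2.5 is then worth about two charts. Also, 40 lies inside the 35.6 to 43.2 range, so literal no overlap could still yield 40 if non-completers were disproportionately unscannable.

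Much of this stands as a limit on size, but it does not rescue the label. The same rounded inputs give 37.5 under the stated assumption. The 17% figure leaves out claustrophobia and is not the rate the plan applies. The plan offers no argument about non-completers. Forty would be a no-overlap figure if the 20% were a rate among study-eligible veterans, but C.1 and C.2.3 both give the base as PIRATE veterans in general.

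The objection does defeat some stronger readings that a reader might infer:

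- **That 37 is the true floor.** It rests on completers being typical of eligible veterans, and the extreme case is 35.6.
- **That 40 is a middling or optimistic overlap case.** It corresponds to 20% overlap, near the low end of the 37.5 to 50 range in the overlap table.
- **That every imaging power figure is compromised.** The figure above 0.99 does not change.

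**Conclusion.** Wrong as written, minor. The imaging sample of 40 does not follow from the no-overlap assumption stated beside it. It is the independence figure. On the plan's own rates, no overlap gives an expected 37 to 38, taking exactly 50 completers who are typical of the eligible pool.

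The cost is 2 to 3 participants, about 0.01 on the detectable correlation, and 2 to 3 points of power at r = 0.38 under the assumed one-sided 0.05 test. A reader might go on to infer that the imaging analysis is underpowered or that its design conclusion fails. The documents do not support that on this ground: at 37 or 38 the study could still detect correlations weaker than the 0.65 to 0.85 cited, as C.3.1.3 concludes. The unstated sidedness matters more, at about 10 points of power at n = 40 (0.785 against 0.682).

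**What to change.** In C.1, replace the worst-case sentence with two labelled figures: about 40 if the two sets of exclusions are independent, and about 37 to 38 if they do not overlap, assuming that completers are typical of eligible veterans.

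In C.3.1.3, keep the n = 40 statement and add the lower case beside it, without calling it a floor. The detectable correlation at the same power is about 0.39 and power at r = 0.38 is about 2 to 3 points lower. State the alpha and sidedness on which these figures rest.

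The cost is wording only, with one stated figure slightly less favourable. No procedure, recruitment target or analysis changes.

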activities for participants is insufficient to explain their gains in communicative function. However, inclusion of a delayed-treatment condition will help establish this more conclusively for the current study. The specifics of the delayed-treatment condition are given in section C.2.1.

PIRATE involves a single 2-day visit to VAPHS 4-6 weeks prior to entry for a medical clearance exam and an initial comprehensive speech-language evaluation and to initiate treatment planning. During this visit, the CAT and PALPA subtests (for confirmation of aphasia diagnosis and for participant classification and treatment planning) are administered. Accepted candidates return to VAPHS at program entry and reside in residential villas at the H.J. Heinz campus of VAPHS for 4 weeks (or 5 weeks in the delayed-treatment condition). At program entry, a second CAT is administered to participants, and PIRATE candidates enrolling in the research study will be given structural MRI scans and the battery of cognitive assessments described above. Therapy is provided in existing, dedicated PIRATE treatment rooms, also located on the Heinz campus. The treatment schedule is five days a week, approximately 5 hours a day, for a total of 25 hours of therapy each week. As described below, PIRATE participants enrolled in the proposed research will receive treatment five days a week, for 4 hours per day. All therapy will be provided by PIRATE-dedicated licensed clinical providers with multiple years of experience delivering aphasia therapy. Participants return to VAPHS for a single follow-up visit 4-6 weeks after program exit.

C.2.1 Treatment:

Over 85% of PIRATE participants to date have received treatment focused on spoken word production. This is also the unit of language function and the output modality targeted in the majority of treatment-neuroanatomy/neuroimaging studies reviewed in section A.2 above, as well as the majority of treatment-cognitive prediction studies reviewed in section A.2. SFA treatment will be implemented as described by Boyle & Coelho⁸ and Boyle.⁹ At the beginning of a treatment trial, the target picture will be placed in the center of a chart containing the following entries: Group, use, action, properties, location, and association. A treatment trial will proceed through the following steps:

1. The participant is asked to name the picture.

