2. Regardless of accuracy in Step 1, the participant is asked to verbally produce at least six distinguishing semantic features of the target. For each feature, the clinician asks a question (e.g., What is it used for?). If the patient responds with an appropriate feature (or features), the clinician repeats the feature, provides optional verbal reinforcement, and writes the response(s) in the chart. The clinician may also prompt the participants to provide additional and/or novel responses before proceeding to the next feature. If the participant is unable to produce an appropriate response, the clinician provides a cloze sentence cue (e.g., This is a kind of _____). If the participant is still unable to provide an appropriate response, the clinician provides the feature verbally and in writing, and asks the participant to repeat the feature name.
3. After all six features are written on the chart, the clinician again asks the participant to name the target picture, regardless of whether the participant has named the picture successfully at any earlier point during the same trial.
4. If the participant is unable to name the picture, the clinician says the name aloud, requires repetition, and requires the participant to verbally produce the six features.

Treatment will be initiated with the first set of 10 treatment items for each patient. The pictures will be presented in a different pseudorandom order on each cycle through the set. If the patient names 90% of the treated items correctly on three of four consecutive probes, treatment on that set will be discontinued and a new set will be introduced. Since naming probes will be given 3 times per week, this criterion ensures that participants who show rapid acquisition will move on to a new treatment set as often as once per week. This in turn means that participants will receive treatment on up to 40 treatment exemplars during their time in the study. This number is greater than the number of treatment exemplars used in the majority of published naming treatment studies recently surveyed by Snell and colleagues^[64].

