hours. All treatment and probe pictures will be selected from the pictures named correctly on fewer than two of those occasions. Four sets of 10 items each will be selected as potential treatment items, along with four sets of 10 related generalization probe items and four sets of 10 unrelated generalization probe items. For each treatment item, a category coordinate will be selected as a generalization probe item. The unrelated generalization probes will be selected from remaining items belonging to categories not occurring within the treatment set. These items will also be selected to minimize associative and other semantic relationships with items in the treatment sets. Within the constraints of semantic relatedness and baseline performance level, we will balance the treatment and generalization sets for lexical frequency and length.

[figure not shown]

Figure 5. Panel A: Expected score for each of the seven 25-item PNT alternate forms, compared to empirical data of 254 aphasic patients. Panel B: Mean Rasch-scaled score for each of the seven alternate PNT forms, for a subsample of 57 aphasic patients.

C.2.2 Probe stimuli, procedures and schedule

Following baseline assessment of all 361 UCSD CRL items, the 40 items selected for training, 40 related items, and 40 unrelated items will be probed at treatment initiation, three times per week during

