Secondary dependent variables for these analyses will include accuracy on untreated related stimuli (accuracy at study exit minus accuracy at study entry) and Rasch-scaled scores for PNT stimuli (scores at exit minus scores at entry). Previous studies have not found any predictive relationships between neuroanatomical or other variables and generalization to untrained stimuli^[9, 20]. However, those studies did not administer treatment in the amounts or intensities provided in PIRATE or in the proposed research. It is possible that more intensive and/or larger doses of aphasia treatment may uncover stronger generalization effects (as well as stronger predictive relationships) than have previously been reported.

C.3.1.1 Group effects on treatment response

Participants will be classified as having primarily phonological, primarily lexical-semantic, or mixed naming impairments, using the methods described in section C.2.3 above. A between-participants analysis of variance will be carried out on the primary and secondary dependent measures of treatment response, with language-impairment group as an independent variable. As predicted by Hypothesis 1a and consistent with previous findings in the naming-treatment literature^[12, 44], we anticipate that there will not be a main effect of language-impairment group on treatment response. The different groups of naming-impaired individuals will show comparable benefit from intensive, semantically-oriented naming treatment. If group differences are found in the ANOVA, we will explore their source using Tukey's multiple comparisons to control type-I error.

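### Related untreated probe words can be spoken and written down during SFA without the plan recording it, so related-item gain may include practised words

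*Combined protocol and SAP*

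**What the plan says.** Stimuli. Section C.2.1 selects the related probes by category: "For each treatment item, a category coordinate will be selected as a generalization probe item". Section C.2.2 fixes the numbers: "the 40 items selected for training, 40 related items, and 40 unrelated items will be probed at treatment initiation". Associative and semantic links to the treated words are minimised for the unrelated probes only.

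Treatment trial. Section C.2.1 states that "the target picture will be placed in the center of a chart containing the following entries: Group, use, action, properties, location, and association". When a response is appropriate, "the clinician repeats the feature, provides optional verbal reinforcement, and writes the response(s) in the chart", and the clinician may then ask for more or different responses. When it is not, "the clinician provides a cloze sentence cue (e.g., This is a kind of" and a blank. If that also fails, "the clinician provides the feature verbally and in writing, and asks the participant to repeat the feature name".

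Records. The daily logs in C.2.1 hold treatment time, exposures to each treated word, number of trials and number of features, novel or recurring. They are not said to hold the words used as features. All sessions are video recorded, and fidelity review checks adherence to the SFA procedure.

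Outcomes. The primary Aim 1 outcome in C.3.1 is change on treated words. A secondary one is "accuracy on untreated related stimuli (accuracy at study exit minus accuracy at study entry"). Unrelated probes are not named there. Section C.3.2 interprets late gains on related words as generalization that emerges after acquisition.

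**The concern.** A word from the same category as the target is a plausible answer to the Association entry, or to a prompt for another response. If that word is the participant's own related probe, it is spoken by the participant, said back by the clinician, possibly reinforced and written on the chart. If the clinician supplies it, the participant repeats it. Nothing in the available text stops this, records it by word or deals with it in analysis. Accepting a probe word as an association would not be a deviation from the SFA procedure, so fidelity review would not flag it.

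At stake is the meaning of related-item gain. The plan treats it as spread of benefit to words that were not trained. If some of those words were practised, the gain mixes generalization with acquisition. The plan guards against exposure elsewhere: it removes 159 Philadelphia Naming Test (PNT) pictures from the stimulus pool and builds seven alternate PNT forms. The related probes have no comparable safeguard.

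**Working it through.** The plan gives no figure for overlap between features and probe words, so there is nothing to reproduce. The check sets the passages against each other and then shows a range.

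**1. Is there a route?** The three elements are all in C.2.1: related probes are category coordinates, Association is a chart entry, and accepted responses are repeated and written with more invited. The route is open but not built in. The chart asks about the target, and the probe picture is not part of the trial.

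**2. Would the data show it?** The log counts features. A count cannot separate a probe word from any other feature. The filled-in charts and the videos could, but no one is assigned to look.

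**3. How large could it be?** Inflation of mean related-item change = f × g, where f is the share of the 40 related words practised (an assumption) and g is the gain per practised word. For g, section A.1.1 gives average improvements of 20 points (semantic impairment) and 37 points (phonological impairment) under semantically oriented treatment. These are taken here as gains on treated targets.

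- f = 5% (2 words): 0.05 × 20 = 1.0 to 0.05 × 37 = 1.85 points
- f = 10% (4 words): 2.0 to 3.7 points
- f = 25% (10 words): 5.0 to 9.25 points

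Ten words is the number of coordinates paired with one treatment set. A word only mentioned as a feature gets no picture and no trial of its own, so using the full target gain probably makes these figures an upper bound for each f.

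**4. Is a non-zero f plausible?** Daily treatment net of breaks is 2 × (120 − 20) = 200 minutes. With 10 items per set and an assumed 10 minutes per trial, that is 20 trials a day, or 2 per item: 10 trials per item in 5 days, 40 in 20 days. The chance that a given coordinate is said at least once in n trials is 1 − (1 − p)^n, with p the assumed chance per trial:

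- n = 10: 0.10, 0.40 and 0.65 for p = 1%, 5% and 10%
- n = 40: 0.33, 0.87 and 0.99 for the same p

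With 5 to 15 minutes per trial, the whole range is 0.07 to about 1.00. Being said once is not the same as being practised, so these are chances of exposure, not values of f. Depending on inputs that the plan does not collect, the effect can be negligible or material.

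**The case against.** The strongest reply is that coordinates are the intended test. Section A.1.1 describes SFA as working through activation that spreads to related concepts, so same-category probes are a legitimate measure of response generalization. This stands: the choice of coordinates is not an error, and only overt practice of the probe word is contamination.

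Second, the route is narrow. A reader might infer that the Group entry also elicits coordinates. The only category cue shown asks what kind of thing the target is, which calls for a superordinate. Probe words were also named correctly on fewer than two of three baseline attempts, which makes spontaneous production less likely. Both points stand; they leave Association and the extra prompts as the main route.

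Third, a reader might infer that exposure builds up as sets are added and so produces the acceleration in Hypothesis 2b. The documents do not support this. Treatment time is constant at 20 hours a week and a set stops when the next begins, so new exposure need not rise. The chance that a word has been said also levels off, and C.3.2 itself expects practised words to decelerate.

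Fourth, acceptable associations may be defined in the published SFA descriptions that C.2.1 follows, and part of section B was not available. That limits any statement about what is absent.

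Finally, unrelated probes, the PNT and connected speech are also collected and are less open to this route. They help, but C.3.2 sets no related-versus-unrelated contrast. Such a contrast would not settle the matter anyway, because spreading activation and overt practice both predict a larger gain on related words. Word-level records are needed to separate the two.

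**Conclusion.** The concern holds as a gap in recording and analysis. Related-item gain could include directly practised words, and the planned log cannot show whether it does. The inflation is about 1 to 9 points if 5% to 25% of related words were practised and gained as much as treated targets. The share is an assumption, and the per-word gain is probably too high. The primary Aim 1 outcome uses treated words only and is unaffected.

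A reader might go further and infer that treatment systematically trains the probe words, or that a falsely significant generalization result is likely. Neither follows. The trial procedure does not call for probe words. The documents give no standard deviation for related-item change, so no error probability for a planned test can be derived.

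**What to change.** In C.2.1:

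- Mark on the existing feature chart each related probe word that the participant produces or the clinician supplies, noting which. Staff who do not treat can do this from the completed chart, using the participant's list of 40 related words. For sessions already delivered, the words can be recovered from the charts if kept, and otherwise from the videos.
- Where two coordinates are equally suitable, avoid one that is a direct associate of the treated word.

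In C.3.1 and C.3.2:

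- Keep the all-items related score as planned.
- Pre-specify a sensitivity analysis of related-item change that leaves out the marked words, dropping the same words at every time point. Report it as a lower bound, because a word produced spontaneously may be one that truly generalized.
- Report unrelated-probe change alongside.

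The cost is a tick on a chart already filled in, a little more analysis and a slightly narrower choice of coordinates. Giving clinicians the 80 untreated probe words and barring their use as features is not recommended. It would alter how features are supplied and make those words salient to the treating staff.
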